5.5 Withdrawal of Subjects and Discontinuation of Study

A subject may voluntarily withdraw or be withdrawn from the study at any time for reasons including, but not limited to, the following:

- Clinically significant abnormal laboratory results or AEs, which rule out continuation of the study drug, as determined by the investigator or the AbbVie Therapeutic Area Medical Director.
- Serious infections (e.g., sepsis) that cannot be adequately controlled within 2 weeks by anti-infective treatment or would put the subject at risk for continued participation in the trial as determined by the Investigator.

- The investigator believes it is in the best interest of the subject.
- The subject requests withdrawal from the study.
- Eligibility criteria violation was noted after the subject started study drug and continuation of the study drug would place the subject at risk.
- Introduction of prohibited medications or dosages and continuation of the study drug would place the subject at risk.
- Subject is non-compliant with tuberculosis (TB) prophylaxis (if applicable) or develops active TB at any time during the study.
- The subject becomes pregnant while on study drug.
- Malignancy, except for localized NMSC or carcinoma in-situ of the cervix.
- Subject is significantly noncompliant with study procedures, which would put the subject at risk for continued participation in the trial.
- Subject develops a gastrointestinal perforation.

In addition, the following discontinuation criteria also apply:

- Subjects not responding to therapy can discontinue study drug (or withdraw from study) at any time for any reason during the study in order to receive standard of care.
- Subjects who demonstrate worsening of joint count (SJC and/or TJC) at 2 consecutive visits (scheduled or unscheduled) should be discontinued from study drug and treated with standard of care at the discretion of the clinician.
- Starting at the Week 18 visit (after the Week 18 assessments have been performed) and at visits thereafter, subjects who fail to achieve at least 20% improvement in TJC and SJC should be discontinued.
- Starting at the Week 18 visit (after the Week 18 assessments have been performed) and at visits thereafter, subjects who fail to achieve $CDAI \leq 10$ should have background medication(s) adjusted or initiated (i.e., initiation of or change in corticosteroids, NSAIDs, acetaminophen or adding or increasing doses in csDMARDs [restricted to oral or parenteral MTX, sulfasalazine, hydroxychloroquine, chloroquine and leflunomide except the combination of MTX and leflunomide is allowed as per local label]).
- Starting at the Week 18 visit (after Week 18 assessments have been performed) and at visits thereafter, intra-articular, intramuscular, intravenous, trigger point or tender point, intra-bursa, and intra-tendon sheath injections of corticosteroids, dosage and frequency per standard of care are allowed. For the analysis of the TJC and SJC, injected joints will be considered "not assessable" for 3 months from the time of the intra-articular injection.
- Starting at the Week 24 visit and at visits thereafter, subjects achieving 20% improvement in TJC and SJC but not achieving $CDAI \leq 10$ should be considered for discontinuation to standard of care at the discretion of the clinician.

Subjects who prematurely discontinue study drug should complete a Premature Discontinuation (PD) Visit as soon as possible, preferably within 2 weeks of discontinuation. See Section 5.6 for information regarding early discontinuation.

For subjects to be considered lost to follow-up, reasonable attempts must be made to obtain information on the subject's final status. At a minimum, 2 telephone calls must be made and 1 certified letter must be sent and documented in the subject's source documentation.

AbbVie may terminate this study prematurely, either in its entirety or at any site. The investigator may also stop the study at his/her site if he/she has safety concerns. If AbbVie terminates the study for safety reasons, AbbVie will promptly notify the investigator.

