3.2 Efficacy Endpoints

There is no primary efficacy endpoint since this is the extension to the feeder Study M16-063. Efficacy endpoints for this study, measured at each study visit, include the following:

- Change in disease activity score (DAS)28 (C-reactive protein [CRP]) from baseline of Study M16-063;
- Proportion of subjects achieving DAS Low Disease Activity (LDA), defined as DAS28 CRP ≤ 3.2 ;
- Proportion of subjects achieving DAS Clinical Remission (CR), defined as DAS28 CRP < 2.6 ;
- Change in clinical disease activity index (CDAI) from baseline of Study M16-063;
- Proportion of subjects achieving LDA based on CDAI criteria, defined as CDAI ≤ 10 ;
- Proportion of subjects achieving CR based on CDAI criteria, defined as CDAI ≤ 2.8 ;
- Proportion of subjects achieving American College of Rheumatology (ACR) 20/50/70 response. A subject will be considered an ACR 20/50/70 responder if:
 - The swollen joint count (SJC) and tender joint count (TJC) have decreased from baseline of Study M16-063 by 20/50/70% or more.
 - At least 3 of the 5 remaining ACR core set measures (i.e., Patient's Assessment of Pain [using visual analog scale, VAS], Patient Global Assessment of Disease Activity [PtGA], Physician Global Assessment of Disease Activity [PhGA], Health Assessment Questionnaire Disability Index [HAQ-DI], and high-sensitivity C-reactive protein [hsCRP]) show reduction of 20/50/70% or more from baseline of Study M16-063.
- Change in individual components of ACR from baseline of Study M16-063, to include:
 - SJC,
 - TJC,

- Patient's Assessment of Pain (using VAS),
 - PtGA,
 - PhGA,
 - HAQ-DI, and
 - hsCRP.
- Change in Morning Stiffness from baseline of Study M16-063.

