7.3 Statistical Analyses for Efficacy

Analysis of efficacy endpoints will be conducted on the FAS based on treatments as randomized for Study M16-063. The analysis will be based on As Observed data, and no imputation will be conducted. The analysis treatment groups will be described as follows indicating from Study M16-063 to extension Study M16-763:

- Group 1: ABBV-599 to ABBV-599
- Group 2: ABBV-105 60 to 105 60 mg
- Group 3: ABBV-105 20 to 105 20 mg
- Group 4: ABBV-105 5 to 105 5 mg
- Group 5: Upadacitinib 15 to Upadacitinib 15 mg, and
- Group 6: Placebo to ABBV-599
- Group 7: All ABBV-599 (Group 1 and 6)

The baseline for all efficacy analyses in this study will be the baseline in Study M16-063.

There is no primary efficacy endpoint and no formal statistical tests will be applied. Only descriptive statistics will be used for all efficacy endpoints. Descriptive statistics will be provided for each treatment group for all visits. These include the number of observations, mean with 95% confidence interval, standard deviation, median, minimum and maximum for continuous endpoints (or the change from baseline measurements), and frequencies and percentages with 95% confidence interval for binary endpoints.

No missing data imputation will be applied. All efficacy analyses will be based on As Observed analysis, and thus a subject who does not have an evaluation at the primary analysis time point will not be included.

Details on efficacy analyses are provided in the SAP.

Sample Size Estimation

This is the LTE study for Study M16-063. All eligible subjects who completed Study M16-063 will be enrolled in this study if the subject signs and dates the informed consent. Based on discontinuation criteria mandating efficacy, it is estimated that 20 - 60% of subjects (i.e., between 40 and 120 subjects) will ultimately complete the LTE.

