### **3.2 Secondary Efficacy Endpoints**

1. Change in disease activity score (DAS)28 (C-reactive protein [CRP]) from baseline of Study M16-063;
2. DAS Low Disease Activity (LDA), defined as DAS28 CRP  $\leq$  3.2;

3. DAS Clinical Remission (CR), defined as DAS28 CRP < 2.6;
4. Change in clinical disease activity index (CDAI) from baseline of Study M16-063;
5. LDA based on CDAI criteria, defined as CDAI  $\leq$  10;
6. CR based on CDAI criteria, defined as CR  $\leq$  2.8;
7. American College of Rheumatology (ACR) 20/50/70 response. A subject will be considered an ACR 20/50/70 responder if:
  - The swollen joint count (SJC) and tender joint count (TJC) have decreased from baseline of Study M16-063 by 20/50/70% or more.
  - At least 3 of the 5 remaining ACR core set measures show reduction of 20/50/70% or more from baseline of Study M16-063.
    - Patient's Assessment of Pain [using visual analog scale, VAS],
    - Patient Global Assessment of Disease Activity [PtGA],
    - Physician Global Assessment of Disease Activity [PhGA],
    - Health Assessment Questionnaire Disability Index [HAQ-DI]
    - High-sensitivity C-reactive protein [hsCRP])
8. Change in individual components of ACR from baseline of Study M16-063, to include:
  - SJC,
  - TJC,
  - Patient's Assessment of Pain (using VAS),
  - PtGA,
  - PhGA,
  - HAQ-DI, and
  - hsCRP.
9. Change in Morning Stiffness Severity (11 point scale) from baseline of Study M16-063.

10. Change in Morning Stiffness Duration (Hours and Minutes) from baseline of Study M16-063

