## **8.2 Handling of Missing Data**

The analysis will be based on As Observed data, and no imputation will be conducted.

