## **8.4 Secondary Efficacy Analyses**

Descriptive statistics will be provided for each treatment group for all visits. These include the number of observations, mean with 95% confidence interval, standard deviation, median, minimum and maximum for continuous endpoints; and frequencies and percentages with 95% confidence interval using Wilson score for binary endpoints.

No missing data imputation will be applied. All efficacy analyses will be based on As Observed (AO) analysis, and thus a subject who does not have an evaluation at the primary analysis time point will not be included.

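### The joint-count stopping criterion overlaps ACR20, so As Observed response among remaining subjects is selected upward and cannot alone show that efficacy is maintained

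*Protocol*

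**What the plan says.** Protocol 5.5 sets the criterion: "subjects who fail to achieve at least 20% improvement in TJC and SJC should be discontinued". It applies from Week 18 onward, and at Week 18 only once that visit's assessments are done. The criterion names no reference baseline, and it does not say whether failing one count is enough or both must fail.

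ACR20 has two parts. The joint part in SAP 3.2 is "The swollen joint count (SJC) and tender joint count (TJC) have decreased from baseline of Study M16-063 by 20/50/70% or more", and Protocol 3.2 agrees. The second part is "At least 3 of the 5 remaining ACR core set measures show reduction of 20/50/70% or more from baseline of Study M16-063"; the stopping criterion does not screen it.

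On missing data, SAP 8.2 says "The analysis will be based on As Observed data, and no imputation will be conducted", and SAP 8.4 says "All efficacy analyses will be based on As Observed (AO) analysis". SAP 8.4 leaves out subjects with no evaluation at a primary analysis time point, a term that neither document defines. SAP 8.5 and 8.6 plan no additional or subgroup analyses.

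Heavy attrition is expected. Protocol 7.3: "Based on discontinuation criteria mandating efficacy, it is estimated that 20 - 60% of subjects" will complete, given as 40 to 120 subjects.

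Protocol 5.6 asks that subjects who stop study drug still be followed at all scheduled visits unless they withdraw consent. They are then treated at the investigator's judgment. The SAP does not say whether those later assessments enter the tables.

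**The concern.** The clinical hypothesis is that efficacy is maintained. Protocol 4.2 makes the main comparison a within-arm one, against the profile seen in the same arm in Study M16-063. Removing failures step by step distorts exactly that kind of comparison over time.

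A subject on drug at Week 24 or later has already passed the joint-count criterion at the preceding visits, if the rule is followed. A subject who failed and no longer attends leaves the denominator as if the missing value carried no information. A subject who failed and still attends contributes a value under other treatment, if such values are used at all. A level or rising ACR20 curve could then be read as lasting or deepening response when part of it is selection.

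Low disease activity, remission and mean DAS28 and CDAI should move in the same direction, because joint counts enter both scores. That is reasoning; it was not simulated.

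**Working it through.** **1. The plan's own figure.** 40/0.20 = 200 and 120/0.60 = 200, so both ends imply 200 subjects. Non-completion of 40–80% is then 80 to 160 subjects. There is no power calculation to reproduce.

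**2. Inputs for an illustration.** The documents give no response rates, so all of these are assumptions. Each subject has a mean improvement from Study M16-063 baseline, normal with mean 40% and SD 30. TJC and SJC each add independent visit noise with SD 20. The criterion is met if both improve by at least 20%. A subject stops after the first visit where either count fails. The visits are those of the protocol.

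**3. Constant effect, no stopped subject observed.**

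| Week | 18 | 24 | 30 | 36 | 48 | 60 |
|---|---|---|---|---|---|---|
| True rate, % | 60 | 60 | 60 | 60 | 60 | 60 |
| Observed, on drug, % | 60 | 82 | 88 | 91 | 93 | 94 |
| Full denominator, stopped = failure, % | 60 | 49 | 44 | 40 | 37 | 35 |

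The third row is the running product of the second: 0.60 × 0.82 = 0.49, and so on to 0.34 at Week 60 from the rounded rates (35% unrounded). Each entry is also the share still on drug at the next visit, so 37% are on drug at the Week 60 visit.

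**4. Some stopped subjects keep attending.** Let a fraction f attend with unchanged response. At Week 60, of every 100 subjects, 37 are on drug and 35 of them pass. The other 63 are off drug and 60 − 35 = 25 of them would pass.

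Observed rate = (35 + 25f)/(37 + 63f)

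- f = 0: 94% (unrounded)
- f = 0.25: 41.25/52.75 = 78%
- f = 0.5: 47.5/68.5 = 69%
- f = 0.8: 55/87.4 = 63%
- f = 1: 60/100 = 60%, no inflation

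**5. Stopping only if both counts fail.** Under a constant effect the on-drug rate goes from 60% to 82%, with about 65% still on drug at Week 60.

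**6. Fading effect** (linear loss from Week 18 to Week 60; stop if either count fails; stopped subjects not observed).
- Loss of 20 points: observed 60, 79, 84, 86, 84, 82%; true 37% at Week 60. Full denominator: 0.60 × 0.79 × 0.84 × 0.86 × 0.84 × 0.82 = 0.24.
- Loss of 40 points: observed 60, 76, 79, 79, 70, 62%; true 18% at Week 60.

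**7. Full ACR20, including 3 of 5 other measures.** A separate simulation used mean improvement 35% or 50% and visit SD 0 to 30 points.
- Flat effect, either count: on-drug ACR20 rises from 47–64% at Week 18 to 89–95% at Week 60, with 30–54% still on drug at that visit.
- Flat effect, both counts: it rises to 65–78%.
- No visit noise: it jumps from 51% to 93% at Week 24 and stays there. That ceiling is the chance of meeting 3 of 5 given the joint criterion.
- 20-point fade, either count: it ends at 73–81% against a true 25–41%.
- 20-point fade, both counts: it ends at 43–56% against the same true range.

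Neither model includes the two-visit worsening rule, the discretionary CDAI stop from Week 24, or background-medication changes. The first two would probably add selection. The third can raise response without any study-drug effect.

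**The case against.** The strongest reply is Protocol 5.6. Stopped subjects are to be followed precisely to limit missing data, and only withdrawal of consent ends follow-up. If all attend, their response is unchanged and their data are used, there is no inflation. This stands in part. It makes 94% an upper extreme. It does not settle the matter: the SAP is silent on using those data, they would reflect other therapy, and Protocol 5.5 also lets non-responders leave the study.

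Second, failures are not invisible. At Week 18 the criterion acts after the assessments, so the failing value counts as non-response at that visit. A premature discontinuation visit includes joint counts. SAP 5.0 tabulates lack of efficacy by group, and SAP 8.4 reports the number of observations. All true, but none of it carries the failure into the response percentages of later visits.

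Third, a full-denominator row is biased too. Under a constant true 60% it falls to 35%, because one chance failure becomes permanent. This stands, and that row should not be used alone.

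Fourth, nothing is tested and there is no primary efficacy endpoint. That limits the stakes to how the maintenance description is read.

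**Conclusion.** The concern holds in a bounded form. The criterion overlaps the joint half of ACR20, efficacy is As Observed only, and the sponsor expects heavy efficacy-driven attrition. As Observed response among remaining subjects therefore cannot by itself support a statement that efficacy is maintained. For the joint criterion with a constant true 60%, the Week 60 reading runs from 60% to about 94%. Where it falls depends on follow-up after stopping, use of those data, and whether one or both counts must fail. All model inputs are assumptions.

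A reader might infer that ACR20 must climb towards 100% by construction, even while the effect fades. The documents do not support that. The 3-of-5 component is not screened and caps ACR20 below 100%, new failures count at the visit where they occur, and under a fade the curve rises and then falls. It stays well above the true rate, and that gap is the real problem.

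**What to change.** Amend SAP 8.4; the stopping rule is untouched.

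1. State whether assessments after stopping study drug enter the As Observed tables, and show the number observed and the number on drug at each visit.
2. For each binary endpoint and visit, add a row with all FAS subjects of the group as denominator. Count as non-responders those already stopped under a Protocol 5.5 efficacy criterion or for lack of efficacy, and all other missing values.
3. For any statement on maintenance, present the As Observed and full-denominator rows together as upper and lower bounds. Note that the latter is conservative because chance failures become permanent (60% to 35% in the constant-effect illustration).
4. Replace the undefined primary analysis time point with each visit.

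Cost: SAP wording, one extra row per binary table plus the counts, and less favourable stated rates. The discontinuation categories in SAP 5.0 have no separate code for the Protocol 5.5 efficacy criteria, so check that such stops are recorded under lack of efficacy and not under other. The added row does not cover mean DAS28 and CDAI; for those, the counts in item 1 are what shows the selection.

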5.6 Follow-Up for Subject Withdrawal from Study

To minimize missing data for efficacy and safety assessments, subjects who prematurely discontinue study drug treatment should continue to be followed for all regularly scheduled visits, unless subjects have decided to discontinue the study participation entirely (withdrawal of informed consent). Subjects should be advised on the continued scientific importance of their data even if they discontinue treatment with study drug early.

Following discontinuation of study drug, the subject should be treated in accordance with the investigator's best clinical judgment irrespective of whether the subject decides to continue participation in the study. In addition, all future rescue- and efficacy-driven discontinuation criteria no longer apply. This includes 20% TJC/SJC calculations at Weeks 12 through 24, Weeks 36 through 40 and Week 48 and thereafter, as well as CDAI calculation at Week 26, if applicable. If at any point a subject no longer wants to provide assessments (withdrawal of informed consent) following discontinuation of study drug, a second PD visit is not required.

If a subject prematurely discontinues study participation (withdrawal of informed consent), the procedures outlined for the PD visit should be completed as soon as possible, preferably within 2 weeks. In addition, if subject is willing, a 30-day follow-up phone call after the last dose of study drug may be completed to ensure all treatment-emergent AEs/SAEs have been resolved.

All attempts must be made to determine the date of the last study drug dose and the primary reason for discontinuation of study drug or study participation. The information will be recorded on the appropriate electronic case report form (eCRF) page. However, these procedures should not interfere with the initiation of any new treatments or therapeutic modalities that the Investigator feels are necessary to treat the subject's condition. Following discontinuation of study drug, the subject should be treated in accordance with the Investigator's best clinical judgment irrespective of whether the subject decides to continue participation in the study.

If a subject withdraws from the main study, biomarker research samples will continue to be stored and analyzed. A subject must contact the study investigator if they no longer want their samples to be stored and analyzed. Once AbbVie is notified, no new information will be collected, no new analysis will be started, and the samples will be destroyed unless a regulatory authority requires AbbVie to keep them. However, if AbbVie (or people or companies working with AbbVie) collected any information or

did any testing before withdrawal, AbbVie (or people or companies working with AbbVie) will still use and disclose such information, use the test results, and keep the data generated from the samples.

5.7 Study Drug

Information about the study drug and placebo used in this study is presented in [Table 2](#).

Table 2. Study Drug

	Investigational Product	Investigational Product	Investigational Product Placebo	Investigational Product Placebo
Investigational Product Name	ABBV-105	Upadacitinib	ABBV-105 Placebo	Upadacitinib Placebo
Active Ingredient	ABBV-105	Upadacitinib	N/A	N/A
Mode/Route of Administration	Oral	Oral	Oral	Oral
Combination Drugs	N/A	N/A	N/A	N/A
Formulation				
Dosage Form	Capsule	Film-Coated Tablet	Capsule	Film-Coated Tablet
Dose and Units	5 mg, 20 mg	15 mg	N/A	N/A
Drug Preparation	N/A	N/A	N/A	N/A
Masking	N/A	N/A	N/A	N/A
Frequency of Administration	Daily	Daily	Daily	Daily
Storage Conditions	Room Temperature (15° to 25°C/ 59° to 77°F)	Room Temperature (15° to 25°C/ 59° to 77°F)	Room Temperature (15° to 25°C/ 59° to 77°F)	Room Temperature (15° to 25°C/ 59° to 77°F)

N/A = not applicable

At each visit where study drug is dispensed, each subject will receive 4 bottles of study drug; three of the bottles will contain capsules of ABBV-105 or matching placebo, and the remaining bottle will contain tablets of upadacitinib or matching placebo, all manufactured by AbbVie. Subjects will be instructed to take 1 capsule of ABBV-105 or placebo from each of the 3 dispensed bottles per day and 1 tablet of upadacitinib or placebo from the remaining dispensed bottle per day. Study drug should be taken orally at approximately the same time each day, with or without food. If subjects should forget to take any of their study drug at their regularly scheduled dosing time, they should take the forgotten dose as soon as they remember, as long as it is at least 10 hours before their next scheduled dose. Otherwise, they should take the next dose at the next scheduled dosing time.

Subject dosing will be recorded on a subject dosing diary. The subject will be instructed to return all drug containers, even if empty, to the study site personnel at each study visit. Study site personnel will document compliance.

AbbVie will not supply drug other than ABBV-105, upadacitinib, and matching placebo for this study. ABBV-105, upadacitinib, and matching placebo will be packaged in bottles with quantities sufficient to accommodate study design. Each kit will be labeled per local requirements, and this label must remain affixed to the kit. Upon receipt, study drug should be stored as specified on the label and kept in a secure location.

Each kit will contain a unique kit number. This kit number is assigned to a subject via interactive response technology (IRT) and encodes the appropriate study drug to be dispensed at the subject's corresponding study visit. Site staff will complete all blank spaces on the label before dispensing to subjects. Study drug will only be used for the conduct of this study.

